4.3. Study Endpoints

4.3.1. **Primary Endpoints**

- Phase 1: Incidences of DLTs and AEs to determine the MTD of up to 2 dosing regimens of ASTX029 and the RP2D and regimen to be taken to Phase 2.
- Phase 2: Clinical activity assessed by ORR according to RECIST v1.1 criteria.

4.3.2. Secondary Endpoint(s)

- PK parameters of ASTX029, including AUC, C_{max} , minimum concentration (C_{min}), time to reach maximum concentration (T_{max}), elimination half-life ($t_{1/2}$), food effect on ASTX029 PK parameters, and other secondary PK parameters of ASTX029 if data permit; analysis of ASTX029 metabolites if applicable.
- Inhibition of pRSK protein in response to ASTX029 treatment in tumor biopsies.
- PFS.
- OS.
- DCR.
- DOR.

4.3.3. Exploratory Endpoint(s)

- Suppression of mutant clones in circulating tumor DNA (ctDNA).
- Explore additional biomarkers of ASTX029 activity.

4.4. Data and Safety Review Committee

For Phase 1, the DSRC will include the principal investigator at each study center; for Phase 2, the DSRC composition will be detailed in the DSRC charter. The DSRC for both phases will also include the Sponsor's medical monitor and other subject matter experts (eg, clinical pharmacologist) as needed. The purpose of the DSRC is to review emerging safety, PK, pharmacodynamic, and preliminary clinical activity data, discuss any safety concerns, and recommend changes in the protocol intended to enhance the safety of subjects or increase the

chances that the study will meet its objectives. Unanimous recommendations for which the only purpose is to enhance the safety of subjects will be implemented immediately, and all investigators and Institutional Review Boards (IRBs)/Independent Ethics Committees (IECs) will be notified regarding such changes.

The DSRC will meet principally by teleconference at least once a month during Phase 1 and at least every 3 months during Phase 2. Additionally, during Phase 1 Part A, it will meet when complete Cycle 1 safety data are available from at least 3 subjects treated at the dose level and regimen being evaluated. After reviewing all available safety, PK, biomarker, and preliminary activity data from at least 3 subjects in each cohort, the DSRC will recommend either increasing the cohort size to 6 or proceeding with either dose escalation or reduction, as appropriate; it will also advise if recruitment into Regimen 2 may be initiated and the dose to be used and if an alternative regimen (Optional Regimen 3) is to be evaluated. The DSRC will also advise when to proceed to Part B (Dose Expansion) and when the Phase 2 portion of the study may be initiated and will recommend the dose and dosing regimen(s) to be used (RDE and RP2D for Phase 1 Part B and Phase 2, respectively).

5. SELECTION AND WITHDRAWAL OF SUBJECTS

5.1. Number of Subjects and Centers

It is anticipated that approximately 300 evaluable subjects will be enrolled in this study if the study fully enrolls both Phases 1 and 2. This includes approximately evaluable 120 subjects in Phase 1 at up to 14 study centers in the US and Europe and up to approximately 180 evaluable subjects in Phase 2 at up to 30 study centers in North America and Europe.

The number of cohorts in Phase 1 Parts A and B and the number of subjects per cohort will be based on emerging safety and PK data and recommendations from the DSRC. The number of subjects in Phase 2 will be based on clinical activity observed and recommendations from the DSRC. More subjects may be enrolled if more dose levels are tested in Part A of the study, if more than 1 cohort is selected for expansion in Part B or if more than the expected number of subpopulations in Cohort F of Phase 2 are expanded.

5.2. Inclusion Criteria

To be eligible for the study, subjects must fulfill all of the following inclusion criteria:

- 1. Able to understand and comply with the study procedures, understand the risks involved in the study, and provide written informed consent before any study-specific procedure is performed.
- 2. Men or women 18 years of age or older.
- 3. Subjects with histologically or cytologically confirmed advanced solid tumors that are metastatic or unresectable, who are refractory or have relapsed after treatment with available therapies or for whom standard life-prolonging measures or approved therapies are not available. In Phase 1 Part B and in the Phase 2 portion of the protocol, subjects must also have documented gene alterations in the MAPK pathway as detailed in Section 4.1.1, Section 4.1.2, and Table 2.
- 4. In Phase 1 Part B of the protocol, subjects must have disease lesions that are amenable to biopsy.
- 5. In the Phase 2 portion of the protocol, subjects must have measurable disease according to Response Evaluation Criteria in Solid Tumors (RECIST) v1.1.
- 6. Eastern Cooperative Oncology Group performance status 0 to 2.
- 7. Acceptable organ function, as evidenced by the following laboratory data:
 - a. AST and alanine aminotransferase (ALT) $\leq 2 \times$ upper limit of normal (ULN) or ≤ 3 ULN in the presence of liver metastases.
 - b. Total serum bilirubin $\leq 1.5 \times ULN$.
 - c. Absolute neutrophil count (ANC) \geq 1500 cells/mm³.
 - d. Platelet count $\geq 100,000$ cells/mm³.
 - e. Calculated creatinine clearance (by the standard Cockcroft-Gault formula) of $\geq 50 \text{ mL/min}$ or glomerular filtration rate of $\geq 50 \text{ mL/min}$.

- 8. Women of child-bearing potential (according to recommendations of the Clinical Trial Facilitation Group [CTFG]; see below* for details) must not be pregnant or breastfeeding and must have a negative pregnancy test (urine or serum as required by local regulations) within 24 hours before the first dose of study treatment. Women of child-bearing potential must agree to the following during the treatment period and for at least 32 days (approximately 5 half-lives of ASTX029 or metabolite plus 30 days) after receipt of last dose of study treatment:
 - a. Refrain from donating eggs (ova, oocytes) for the purpose of reproduction.
 - b. Use a contraceptive method** that is highly effective with a failure rate of <1% per year), with low user dependency. The investigator should evaluate the effectiveness of the contraceptive method before the first dose of study treatment. The investigator is responsible for review of medical history, menstrual history, and recent sexual activity to decrease the risk for inclusion of a woman with an early undetected pregnancy.
- 9. Men with a pregnant partner or non-pregnant partner who is a woman of childbearing potential must agree to the following during the treatment period and for at least 92 days (approximately 5 half-lives of ASTX029 or metabolite plus 90 days) after receipt of last dose of study treatment:
 - a. Refrain from donating sperm.
 - b. Be abstinent from heterosexual intercourse as their preferred and usual lifestyle (abstinent on a long term and persistent basis) and to remain abstinent OR to use a male condom when having sexual intercourse with a woman of childbearing potential (according to recommendations of the CTFG; see below* for details) who is not currently pregnant, and the female partner should be advised of the benefit of using an additional highly effective contraceptive method** with a failure rate of <1% per year as a condom may break or leak. The investigator should evaluate the effectiveness of the contraceptive method before the first dose of study treatment.

*According to recommendations of the CTFG (http://www.hma.eu /fileadmin/dateien /Human_Medicines/01-About_HMA/Working_Groups/CTFG/2020_09_HMA_ CTFG_Contraception_guidance_Version_1.1_updated.pdf), a woman is considered of childbearing potential (ie, fertile) following menarche and until becoming postmenopausal, unless permanently sterile. Permanent sterilization methods include hysterectomy, bilateral salpingectomy, and bilateral oophorectomy. A man is considered fertile after puberty unless permanently sterile by bilateral orchidectomy.

**Contraceptive measures that may be considered highly effective comprise combined hormonal contraception (oral, vaginal, or transdermal) or progestogen-only hormonal contraception (oral, injectable, implantable) associated with inhibition of ovulation, intrauterine device, intrauterine hormone-releasing system, bilateral tubal occlusion, sexual abstinence, and surgically successful vasectomy. Abstinence is acceptable only if it is consistent with the preferred and usual lifestyle of the subject. Periodic abstinence (eg, calendar, ovulation, symptothermal, or postovulation methods) and withdrawal are not acceptable methods of birth control.

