- 3. Subjects with histologically or cytologically confirmed advanced solid tumors that are metastatic or unresectable, who are refractory or have relapsed after treatment with available therapies or for whom standard life-prolonging measures or approved therapies are not available. In Phase 1 Part B and in the Phase 2 portion of the protocol, subjects must also have documented gene alterations in the MAPK pathway.
- 4. In Phase 1 Part B of the protocol, subjects must have disease lesions that are amenable to biopsy.
- 5. In the Phase 2 portion of the protocol, subjects must have measurable disease according to Response Evaluation Criteria in Solid Tumors (RECIST) v1.1.
- 6. Eastern Cooperative Oncology Group performance status 0 to 2.
- 7. Acceptable organ function, as evidenced by the following laboratory data:
 - a) Aspartate aminotransferase (AST) and alanine aminotransferase (ALT) ≤2×upper limit of normal (ULN) or ≤3 ULN in the presence of liver metastases.
 - b) Total serum bilirubin $\leq 1.5 \times ULN$.
 - c) Absolute neutrophil count (ANC) \geq 1500 cells/mm³.
 - d) Platelet count $\geq 100,000$ cells/mm³.

- e) Calculated creatinine clearance (by the standard Cockcroft-Gault formula) of ≥50 mL/min or glomerular filtration rate of ≥50 mL/min.
- 8. Women of child-bearing potential (according to recommendations of the Clinical Trial Facilitation Group [CTFG]; see protocol for details) must not be pregnant or breastfeeding and must have a negative pregnancy test within 24 hours before the first dose of study treatment. While receiving study treatment and for at least 32 days (approximately 5 half-lives of ASTX029 or metabolite plus 30 days after completing treatment, women of child-bearing potential must agree to practice highly effective contraceptive measures (as described in the protocol) and must refrain from donating eggs (ova, oocytes) for the purpose of reproduction.
- 9. Men with a pregnant partner or nonpregnant partner who is a woman of child-bearing potential (according to recommendations of the CTFG; see protocol for details) must agree to, during the treatment period and for at least 92 days (approximately 5 half-lives of ASTX029 or metabolite plus 90 days) after completing treatment, practice highly effective contraceptive measures (as described in the protocol), not to father a child, and to refrain from donating sperm.

Exclusion Criteria

Subjects meeting any of the following exclusion criteria will be excluded from the study:

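### Inclusion 9 names men with a pregnant partner, but 9b requires a condom only with a partner who is not pregnant, so no barrier is required with her during dosing

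*Protocol*

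**What the plan says.** The relevant text is Protocol Section 5.2, inclusion criterion 9, with its two footnotes.

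- **Stem.** "Men with a pregnant partner or non-pregnant partner who is a woman of childbearing potential must agree to the following". The obligations run through treatment and for "at least 92 days (approximately 5 half-lives of ASTX029 or metabolite plus 90 days) after receipt of last dose of study treatment".
- **9a.** No sperm donation. This binds every man covered by the stem.
- **9b, first option.** "Be abstinent from heterosexual intercourse as their preferred and usual lifestyle (abstinent on a long term and persistent basis) and to remain abstinent OR". The double-asterisk note repeats the limit: "Abstinence is acceptable only if it is consistent with the preferred and usual lifestyle of the subject".
- **9b, second option.** A male condom with a woman of childbearing potential, restricted by "see below* for details) who is not currently pregnant, and the female partner should be advised of the benefit" of adding a highly effective method.
- **Highly effective methods (double-asterisk note).** Hormonal methods, then "intrauterine device, intrauterine hormone-releasing system, bilateral tubal occlusion, sexual abstinence, and surgically successful vasectomy". No condom or other barrier is listed.
- **Synopsis, inclusion 9.** Men with a pregnant or a non-pregnant partner must "practice highly effective contraceptive measures (as described in the protocol), not to father a child, and to refrain from donating sperm".
- **Section 10.2.3.** Covers reporting of partner pregnancies, prompt notification by the subject, and counselling by the investigator. It stops treatment only for female subjects who become pregnant.

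**The concern.** The stem brings in men with a pregnant partner, but the only condom requirement in the protocol excludes intercourse with her. A sexually active man can meet every word of criterion 9 and still have unprotected intercourse with his pregnant partner while taking the drug every day.

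The same happens if she conceives on study. Read literally, 9b drops the condom duty with her from that point, while he may continue dosing. The people exposed would be a partner and a fetus who are not trial subjects. The protocol already requires a barrier with non-pregnant partners, so the protection is missing for one named group only.

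This is a participant-protection point. It touches no endpoint, sample size or analysis.

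**Working it through.** The documents state no figure to reproduce. The check is a reading of the clauses together, plus one short calculation of how long the gap can last.

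**Step 1: what binds a non-abstinent man whose only partner is pregnant**

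| Text | Applies to him? | Requires a barrier with her? |
|---|---|---|
| Stem of 9 | Yes, he is named | No, it only introduces a and b |
| 9a, sperm donation | Yes | No |
| 9b, abstinence | Not open to him; it must already be his habit | No |
| 9b, condom | Not with her while she is pregnant | No |
| Synopsis 9 | Yes, but defers to the body | No; a listed method such as vasectomy would satisfy it |
| List of highly effective methods | By reference only | No barrier method on the list |
| Section 10.2.3 | Yes, if she conceives on study | No; notification, reporting and counselling only |

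Within Section 5.2, only 9a operates for him until she delivers.

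**Step 2: whether the qualifier creates the gap.** The single-asterisk note treats a woman as of childbearing potential from menarche to menopause unless permanently sterile. A pregnant partner normally fits that definition. Without the added restriction to women who are not pregnant, the condom clause would reach her.

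**Step 3: how long the gap can last.** The half-life allowance can be recovered from the two follow-up periods.

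- Men: 92 − 90 = 2 days.
- Women (inclusion 8, "at least 32 days (approximately 5 half-lives of ASTX029 or metabolite plus 30 days) after receipt of last dose of study treatment"): 32 − 30 = 2 days.

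Both give about 2 days for five half-lives. The exposure-relevant window is therefore dosing days plus about 2, ending sooner if she delivers. Section 7.3 sets continuous dosing in 21-day cycles for the recommended Phase 2 dose. Two cycle counts, chosen here only for illustration, assume no interruption:

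- 2 cycles: 2 × 21 + 2 = 44 days at most.
- 6 cycles: 6 × 21 + 2 = 128 days at most.

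The lower end depends on how far the pregnancy has advanced at first dose, which the documents do not give. These figures measure time, not risk.

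**The case against.** The strongest reply is that the exemption may be deliberate. The restriction to non-pregnant women is specific. Item 9b reads as a clause about preventing conception: a condom, then advice on a second method because a condom can fail. Once the partner is pregnant, that purpose is spent. The stem still has work to do for these men. 9a binds them, and 9b binds them with any non-pregnant partner, including the same partner after delivery if that falls within treatment plus 92 days. This stands: a reader might infer that the sponsor meant to protect the pregnant partner and made a drafting slip, but the text does not establish that. Synopsis 9, which asks men with a pregnant partner to use contraception, shows inconsistency rather than clear intent either way.

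A second reply is that no harm has been shown. Section 1.3.2.4 reports negative genotoxicity tests, and Section 1.3.2.1 reports very high plasma protein binding. Neither settles fetal risk through semen. But the documents give no semen concentration, and although the protocol reports no embryo-fetal study, Section 1.3 refers to the Investigator Brochure for complete information. A reader might infer that no such study exists, or that the fetus is at known risk. The documents support neither.

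Third, Section 10.2.3 offers partial mitigation. The subject must tell the investigator at once if his partner becomes pregnant, and the investigator should counsel on possible fetal effects. That is not a barrier, and it does not clearly reach a partner who is already pregnant at entry.

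What survives is the literal gap, which none of these replies closes.

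**Conclusion.** The concern holds in limited form. For a non-abstinent man whose only partner is pregnant, criterion 9 leaves only the sperm-donation ban until delivery. Nothing else in the protocol requires a barrier with her during dosing, whether she was pregnant at entry or conceives on study.

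It would overstate the point to say that 9b imposes nothing on such men. It still applies with any non-pregnant partner of childbearing potential, and with the same partner once she has delivered.

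The gap runs for the overlap of pregnancy and dosing, plus about 2 days if the protocol's half-life allowance is taken at face value. The number of men affected and the size of the fetal risk are not in the documents. What men are told at consent cannot be checked here. Confidence is therefore high on the wording and only moderate on its practical importance. No estimate, test or operating characteristic changes. The case for acting is that the safer rule costs almost nothing.

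**What to change.** **Item 9b.** Keep the abstinence option and its limit as they are. Change the condom clause so that it covers two groups: a partner who is pregnant, and a non-pregnant woman of childbearing potential. Retain the reference to the Clinical Trial Facilitation Group definition. Direct the advice about an additional highly effective method to non-pregnant partners only. The period in the stem, treatment plus 92 days, needs no change.

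**Synopsis 9.** Adding a condom sentence is not enough. The synopsis makes highly effective contraception mandatory, whereas 9b requires abstinence or a condom and only advises the second method. Replace the synopsis contraception wording with the revised 9b requirement, and keep its bans on sperm donation and on fathering a child.

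**Cost.** A small wording amendment, a consent-form update where the criterion is repeated, and a minor added burden on the men affected. There are no extra visits, procedures or subjects.

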5.3. Exclusion Criteria

Subjects meeting any of the following criteria will be excluded from the study:

1. Hypersensitivity to ASTX029 or excipients of the drug product.

- 2. Poor medical risk in the investigator's opinion because of systemic diseases in addition to the cancer under study, for example, uncontrolled infections.
- 3. Life-threatening illness, significant organ system dysfunction, or other condition that, in the investigator's opinion, could compromise subject safety or the integrity of study outcomes or interfere with the absorption or metabolism of ASTX029.
- 4. Prior anticancer treatments or therapies within the indicated time window prior to first dose of study treatment (ASTX029), as follows:
 - a. Cytotoxic chemotherapy or radiotherapy within 3 weeks prior. Palliative radiotherapy to a single lesion within 2 weeks prior. Any encountered treatment-related toxicities (excepting alopecia) not stabilized or resolved to ≤Grade 1.
 - b. Monoclonal antibodies or biologics within 4 weeks prior. Any encountered treatmentrelated toxicities not stabilized or resolved to ≤Grade 1.
 - c. Molecularly targeted drug or other investigational drugs, without the potential for delayed toxicity, within 4 weeks of the first dose of study treatment or 5 half-lives (minimum 14 days), whichever is shorter. Any encountered treatment-related toxicities (excepting alopecia) not stabilized or resolved to ≤Grade 1.
- 5. Prior treatment with ERK inhibitors.
- 6. History of, or at risk for, cardiac disease, as evidenced by 1 or more of the following conditions:
 - a. Abnormal left ventricular ejection fraction (LVEF; <50%) on echocardiogram (ECHO) or multiple-gated acquisition (MUGA) scan.
 - b. Congestive cardiac failure of ≥Grade 3 severity according to New York Heart Association (NYHA) functional classification defined as patients with marked limitation of activity and who are comfortable only at rest.
 - c. Unstable cardiac disease including unstable angina or hypertension as defined by the need for overnight hospital admission within the last 3 months (90 days).
 - d. History or evidence of long QT interval corrected for heart rate (QTc), ventricular arrhythmias including ventricular bigeminy, complete left bundle branch block, clinically significant bradyarrhythmias such as sick sinus syndrome, second- and third-degree atrioventricular (AV) block, presence of cardiac pacemaker or defibrillator, or other significant arrhythmias.
 - e. Screening 12-lead ECG with measurable QTc interval of ≥470 msec. (Fridericia's formula should be used to calculate the QTc interval throughout the study.)
- 7. Known history of human immunodeficiency virus (HIV) infection or seropositive results consistent with active hepatitis B virus (HBV) or active hepatitis C virus (HCV) infection.
- 8. Known brain metastases, unless previously treated and stable for at least 3 months with or without steroids.
- 9. Known significant mental illness or other conditions, such as active alcohol or other substance abuse that, in the opinion of the investigator, predispose the subject to high risk of noncompliance with the protocol treatment or assessments.

- 10. History or current evidence/risk of retinal vein occlusion (RVO) or central serous retinopathy (CSR) including:
 - a. Presence of predisposing factors to RVO or CSR (eg, uncontrolled glaucoma or ocular hypertension, uncontrolled diabetes mellitus) or
 - b. Visible retinal pathology as assessed by ophthalmic examination at screening that is considered a risk factor for RVO or CSR such as:
 - Evidence of optic disc cupping or
 - Evidence of new visual field defects on automated perimetry or
 - Intraocular pressure >21 mmHg as measured by tonography.

5.4. Treatment Discontinuation and Withdrawal of Subjects

Subjects who discontinue study treatment will be followed up for important study data, as described below, unless they withdraw consent from further follow-up.

5.4.1. Discontinuation From Study Treatment

Subjects may permanently discontinue study treatment at any time (**note: subjects who experience disease progression while receiving ASTX029 should not remain on study treatment**). Subjects who discontinue study treatment will still continue study follow-up procedures until death, or until they withdraw consent or the study is closed. Investigators are encouraged to assess all subjects according to the study protocol even after discontinuation from study treatment. Possible reasons for discontinuation of study treatment include the following:

- Investigators can discontinue subjects from study treatment in case of unacceptable toxicity, non-compliance, disease progression requiring alternative therapy, or if the investigator determines it is in the subject's best interest.
- The Sponsor may require that a subject is discontinued from treatment for safety reasons or for noncompliance.

In all cases, the reason(s) for discontinuation from study treatment must be recorded in the source document and on the relevant page of the subject's electronic case report form (eCRF).

It is important to obtain protocol-specified follow-up information on any subject discontinued from study treatment. For subjects who discontinue study treatment, the investigator should review the follow-up procedures with the subject, including the number of visits, the specific procedures to be done, and the total length of the follow-up period. If at all possible, subjects should undergo all safety and preliminary clinical activity evaluations at the Tx Term visit (Section 9.4.13) and the 30-day Safety Follow-up visit (Section 9.4.14). Section 10 describes follow-up for AEs. At minimum, subjects should be followed up for safety until 30 days after the last dose of study treatment (see Section 10.3).

Subjects who agree to remain enrolled in the study after discontinuing study treatment and completing the 30-day Safety Follow-up visit will be contacted by telephone for health status information every 3 months until death, withdrawal of consent, or the end of study, whichever occurs first (see Section 9.4.15).

